In order to have 50 smokers complete all sessions, we will enroll (consent) 150 participants. We anticipate approximately 50% (n=75) of those who consent will meet final eligibility criteria. Of the 75 who are eligible, we

conservatively estimate 25% attrition to have 50 smokers complete the study. Participants will first be screened over the phone and then complete an in-person Intake to ensure final eligibility. Enrolled participants will be randomized to receive ramelteon and placebo in counterbalanced order. Participants will be told that this study includes two practice quit attempts with an FDA-approved medication that is being tested as a possible new treatment for smoking cessation.

3. Key Inclusion Criteria

Smokers ages 18-65, who have smoked at least 10 cigarettes per day for the past 6 months, will be eligible to participate. They must be able to provide informed consent, and express interest in quitting smoking in the next 2 to 4 months. Using a scale from 0 to 100, they must rate their confidence that they will make a quit attempt in the next 2 months a 50 or higher. Following the current study, participants will be referred to a free smoking cessation program. Those who wish to quit sooner can be referred directly to another program.

4. Key Exclusion Criteria

Subjects who self-report and/or present with the following criteria will not be eligible to participate in the study.

Smoking Behavior:

1. Current enrollment in a smoking cessation program, or use of other smoking cessation medications in the last month or plans to do either in the next 2 months.
2. Daily use of chewing tobacco, snuff and/or snus, or electronic cigarettes.
3. Provide a carbon monoxide (CO) breath sample reading less than 10 parts per million (ppm) at Intake.

Alcohol/Drugs:

1. Self-report current alcohol consumption that exceeds 25 standard drinks/week over the past 6 months. Subjects will be told to limit or avoid the use of alcohol while in the study to avoid any adverse reactions to the study medication.
2. Self-reports substance use disorders (abuse or dependence involving alcohol, opiates, cocaine or other stimulants, or benzodiazepines; not nicotine) in the last 6 months.
3. Self-reports daily use of marijuana. Individuals who report occasional use must agree to refrain from use for the duration of the study.
4. Providing a breath alcohol concentration (BrAC) reading of greater than or equal to 0.01 during any session.

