3.4 Smoking Outcomes

Smoking Rate (TLFB). We will assess the number of cigarettes smoked on each day throughout the study. A standard timeline follow-back (TLFB) method will be used [67], as we have done previously [68] to assess self-reported smoking rate. During each quit week, abstinence will be assessed daily by self-report of no smoking at all over the prior 24 hours and an expired-air CO less than 5 ppm (except for the Monday visit when CO may be less than 10ppm or less than 50% Baseline CO). This stringent biochemical criterion for validating smoking cessation has been shown to be more sensitive to detect smoking and specific to verify abstinence than higher CO cut-offs [69].

Carbon Monoxide. Carbon monoxide (CO) measures will be made using a Vitalograph Breath CO Analyzer (McNeil International, Inc., Lenexa, KS). The manufacturer will have calibrated this device within the past year. A new, disposable cardboard mouthpiece will be provided for each participant. The device has a digital screen which reports CO levels in parts per million (ppm). Participants will be asked to provide a CO breath sample by taking a large breath then exhaling twice. Then, they will take another deep breath and hold their breath for 10 seconds, as per the recommendations of the American Thoracic Society. Then, when instructed to do so, participants will exhale as forcefully and as long as they are comfortably capable. The largest value displayed is recorded during all CO breath samples. CO breath samples will be collected at each study visit. At the Intake, participants must have CO readings greater than or equal to 10ppm in order to be eligible for the study.

2. Statistical Analysis

Sample size.

Effect sizes for power analyses were derived from prior work on TN effects on days of abstinence (Aim 1) [6], studies demonstrating RAM's effects on sleep (Aim 2), and our preliminary data. All significance levels will be set at 0.05. Our primary hypothesis is that RAM will increase the number of days abstinent (out of 5), compared to placebo. In prior validation work, the average number of days abstinent for TN was 2.0 ± 0.3 [6]. Fifty subjects provide 80% power to detect a difference of 0.55 days between RAM and PLA, using a SD of 1.36 and a within-subjects correlation of 0.78 [31].

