For Aim 2, meta-analyses indicate that RAM is associated with reducing SOL by 4.3 min and increasing sleep efficiency by 4.42% [70]. Our preliminary data suggest that TN increases sleep disturbance by 58% ($d=0.28$) in abstinent smokers and that abstinence increases SOL by ~5 min and decreases sleep efficiency by ~5%. Fifty subjects provide 80% power to detect differences of 6 min in SOL and 5% in sleep efficiency between RAM and PLA, using a within-subject correlation between 0.4 and 0.8. Thus, Aims 1 and 2 are sufficiently powered.

Statistical Analysis.

For Aim 1 (H1), a within-subject ANOVA will test the primary hypothesis for effects of RAM (vs. PLA) on number of days abstinent during the quit week.

For Aim 2 (H2a), separate 2 drug (RAM vs. PLA) x 2 week (baseline vs. quit week) repeated measures ANOVAs will test the effects of RAM on SOL and sleep efficiency. Drug and week are within-subject factors and sleep measures will be averaged across days within each baseline and quit week. We are primarily interested in the drug x week interaction to test whether RAM (vs. placebo) attenuates sleep disturbance during the quit week, relative to baseline. Thus, each period has its own baseline control comparison. A supplemental analysis will include only days during the quit week when subjects are abstinent.

For Aim H2b, linear regression models will test whether sleep disturbance predicts number of days abstinent and

whether this relationship varies by treatment. Models will include covariates (e.g., baseline depression/anxiety, FTND, sex, and age). We will also examine correlations between sleep disturbance data and nicotine withdrawal and depression/anxiety symptoms in both groups.

3. Confidentiality

All participant information will be kept in a secure filing cabinet that is accessible only to authorized study personnel. All study databases containing participant information will be password protected, and accessible only to authorized study personnel. Any study communications made by e-mail will use ID numbers and not include names or other personal information. All data sets will use ID numbers only.

How will confidentiality of data be maintained? Check all that apply.

- Paper-based records will be kept in a secure location and only be accessible to personnel involved in the study.
- Computer-based files will only be made available to personnel involved in the study through the use of access privileges and passwords.

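### Does the primary power statement (SD 1.36, correlation 0.78, 0.55 days, 50 completers) contradict itself?

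*Combined protocol and SAP*

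**What the plan says.** The Sample size paragraph, under Statistical Analysis in the combined protocol and SAP, rests the primary outcome (days abstinent out of five) on one sentence: "Fifty subjects provide 80% power to detect a difference of 0.55 days between RAM and PLA, using a SD of 1.36". It gives the inputs as "using a SD of 1.36 and a within-subjects correlation of 0.78" and cites a published trial for them. On the test level it says only "All significance levels will be set at 0.05", without giving sidedness. For the analysis, "a within-subject ANOVA will test the primary hypothesis for effects of RAM (vs. PLA) on number of days abstinent during the quit week". Fifty is a completer target: under Accrual, "In order to have 50 smokers complete all sessions, we will enroll (consent) 150 participants". After a similar calculation for the sleep outcomes, the section concludes: "Thus, Aims 1 and 2 are sufficiently powered".

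No other part of the document gives an SD for days abstinent. The nearest figure is a mean of 2.0 ± 0.3 days on nicotine patch from earlier validation work. The ± is not labelled and no sample size is given with it.

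**The concern.** An SD and a within-subject correlation are usually quoted together because the correlation converts a per-condition SD into the SD of the paired difference. A reader who makes that conversion gets a detectable difference about a third smaller than the plan's, and concludes that the inputs and the result do not match.

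This sentence is the only quantitative support for 50 completers on the primary outcome. If it were wrong, the claim that Aim 1 is adequately powered would lose its basis. The two readings also imply different designs: a detectable difference of 0.36 or 0.55 days, and 24 or 50 completers needed for 80% power at 0.55. The abstract says the data will support a larger trial, so someone could reuse 1.36 and 0.78 in the wrong combination when planning it.

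**Working it through.** **Inputs, all from the Sample size paragraph:** n = 50 completers, power 80%, alpha 0.05, difference 0.55 days, SD 1.36, correlation r = 0.78. Two-sided testing is assumed. With two conditions the planned within-subject ANOVA is equivalent to a paired t-test, and its F test is two-sided. Power comes from the noncentral t with 49 degrees of freedom and noncentrality difference × √n / SD_diff.

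**Step 1. Reproduce the plan's figure, taking 1.36 as the SD of the paired difference.**
- Noncentrality at 0.55 days: 0.55 × √50 / 1.36 = 2.86.
- Power at 0.55 days: 80.04% with n = 50 and 79.2% with n = 49, so 50 is the smallest n reaching 80%.
- Detectable difference at 80% power: 0.5497 days, which rounds to the stated 0.55.

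Sample size, power, difference and SD all agree.

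**Step 2. Take 1.36 as the per-condition SD and apply 0.78.**
- SD_diff = 1.36 × √(2 × (1 − 0.78)) = 1.36 × √0.44 = 0.902.
- Noncentrality at 0.55 days: 0.55 × √50 / 0.902 = 4.31, giving 98.8% power.
- Detectable difference at 80% power: 0.365 days. Completers needed for 80% power at 0.55: 24.
- Rounding in the inputs (SD 1.355 to 1.365, r 0.775 to 0.785) moves the detectable difference only between 0.359 and 0.370, so rounding does not explain the gap to 0.55.
- A per-condition SD of 1.36 would give 0.55 only with r = 0.50, which contradicts the stated 0.78.

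**Step 3. Is the reading in step 1 compatible with 0.78?** If 1.36 already incorporates the correlation, the per-condition SD is 1.36 / √0.44 = 2.05 days. For an outcome between 0 and 5 with mean 2.0, the largest possible SD is √(2 × 3) = 2.45. So 2.05 is feasible, and 0.78 can record how 1.36 was obtained.

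**Step 4. Sidedness and degrees of freedom.** A one-sided 0.05 test gives 0.485 days under step 1 and 0.322 under step 2. Neither is 0.55, so the plan's own number points to a two-sided test. Using 48 degrees of freedom, as with a period term, gives 0.550 and 0.365, so nothing changes.

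| Reading of 1.36 | SD of difference | Detectable difference, n = 50 | Power at 0.55 days | n for 80% at 0.55 |
|---|---|---|---|---|
| SD of paired difference | 1.36 | 0.550 | 80.0% | 50 |
| Per-condition SD, r = 0.78 applied | 0.902 | 0.365 | 98.8% | 24 |

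**The case for a change.** The strongest case for asking for a change is that the sentence presents two inputs jointly and, combined in the usual way, they do not give the stated result. Nothing else in the document settles the matter. The 2.0 ± 0.3 does not help: if 0.3 is a standard error, the implied SD is 1.34 for an assumed n of 20 and 2.03 for an assumed n of 46, so it could support either reading.

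The readings also differ in robustness. With a per-condition SD of 1.36, the correlation could fall to 0.50 and power at 0.55 days would still be 80%. With a per-condition SD of 2.05 there is no slack: power is about 55% at r = 0.60 (SD_diff = 2.05 × √0.80 = 1.83) and about 46% at r = 0.50 (SD_diff = 2.05). The plan itself allows correlations from 0.4 to 0.8 for its sleep outcomes.

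The labelling point stands: the text does not say which SD is meant, and one word would have settled it. The rest does not carry a change. The readings are not equally likely, since one misses by a third and the other returns the stated difference, power and sample size together. Sensitivity to a lower correlation is a general feature of crossover planning; it is no evidence that 0.78 is wrong or that 50 completers are too few. The risk of misuse in a later trial concerns that trial's planning, which would have this trial's own paired data to draw on.

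**Conclusion.** The concern does not call for a change. The documents do not show 0.55 days to be wrong: it follows exactly from 50 completers and 80% power when 1.36 is the SD of the paired difference, the quantity a two-condition within-subject test uses. The omission is one of labelling, and a statistician can resolve it by running the calculation both ways.

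Nothing in the trial depends on the answer. At the stated inputs, power at 0.55 days is 80.0% under one reading and 98.8% under the other, so the claim of adequate power for Aim 1 holds either way at that difference. If 1.36 is in fact per condition, the plan understates its own sensitivity (0.36 rather than 0.55 days), which is conservative. The completer target, the primary test and its level stay the same, so adding a label would improve the record without improving the trial.

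This conclusion assumes two-sided 0.05, 50 completers with both quit weeks observed, and the plan's SD and correlation taken at face value. The source cited for them was not available. The preference for the paired-difference reading is an inference from how closely the numbers fit; the text does not state it.

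### Aim 2 is declared adequately powered from an unexplained 6 min difference in sleep onset latency, above the plan's own cited 4.3 and ~5 min, with no SD and no link to the test planned

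*Combined protocol and SAP*

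**What the plan says.** All of this is in the combined protocol and SAP, section 2, Statistical Analysis, which follows section 3.4, Smoking Outcomes.

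- **Source of the effect sizes.** For Aim 2 the plan names studies of ramelteon's "effects on sleep (Aim 2), and our preliminary data".
- **Cited effects.** Meta-analyses are said to show that "RAM is associated with reducing SOL by 4.3 min and increasing sleep efficiency by 4.42" per cent. Preliminary data are said to show that "abstinence increases SOL by ~5 min and decreases sleep efficiency by ~5" per cent. The paragraph also reports a patch-related rise in sleep disturbance of 58% (d=0.28), not expressed in minutes or in efficiency points.
- **Power statement.** "Fifty subjects provide 80% power to detect differences of 6 min in SOL and 5% in sleep efficiency between RAM and PLA". The only further input is a range of correlations from 0.4 to 0.8, not a single value. No SD is given for either sleep outcome. For Aim 1, by contrast, the plan reports "using a SD of 1.36 and a within-subjects correlation of 0.78".
- **Significance level.** "All significance levels will be set at 0.05". The number of sides is not stated.
- **Conclusion.** "Thus, Aims 1 and 2 are sufficiently powered".
- **Planned test.** Under H2a, each sleep measure goes into a 2 (drug) by 2 (baseline or quit week) within-subject ANOVA, and the drug-by-week interaction is named as the effect of main interest.

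**The concern.** The 6 min used for SOL is larger than both SOL effects that the plan cites, and nothing explains the choice. Power at 6 min does not show that the study can detect 4.3 or 5 min. Without an SD the 80% cannot be checked. The power sentence speaks only of a difference between ramelteon and placebo, so it is unclear whether it refers to the quit-week difference or to the interaction. The interaction is a valid test; the gap is that the power figure is not tied to it.

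The abstract says the data will be the basis for a larger Phase IIb trial, and shorter SOL is part of the proposed mechanism. If the plan says the aim has enough power, a non-significant SOL result could be read as evidence against the cited ramelteon effect, although the plan never shows that the test could detect it.

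**Working it through.** **Inputs.** From the plan: n=50 completers; alpha 0.05; 80% power; differences of 6 min and 5%; cited effects of 4.3 min, about 5 min and 4.42%; correlation 0.4 to 0.8. Assumed: a two-sided paired t-test on within-subject contrasts (noncentral t), and sleep efficiency in percentage points.

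**1. The plan's own figure.** The 80% cannot be reproduced forwards, because no sleep SD is stated. It can only be inverted. With n=50, 80% power needs a standardised difference (difference / SD of the contrast) of 0.4042. The 80% therefore implies a contrast SD of
- SOL: 6 / 0.4042 = 14.8 min
- sleep efficiency: 5 / 0.4042 = 12.4 points

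**2. Power at the cited effects, if the 80% is exact for the tested contrast.**

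| Effect | Standardised | Power |
|---|---|---|
| SOL 4.3 min | 4.3/14.84 = 0.290 | 52% |
| SOL 5 min | 5/14.84 = 0.337 | 65% |
| Efficiency 4.42 points | 4.42/12.37 = 0.357 | 70% |

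A one-sided test inverted the same way gives 55% at 4.3 min, so the number of sides is not what drives the result.

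**3. If the 80% is a floor set at r=0.4.** Take a simple paired difference, SD of difference = SD × √(2(1−r)), with the per-condition SD fixed. At r=0.4 the SD is 14.84/√1.2 = 13.55 min. At r=0.8 the SD of the difference is 13.55 × √0.4 = 8.57 min, and power at 4.3 min is 94%. So power at 4.3 min runs from 52% to 94%. It reaches 80% when the SD of the difference falls to 10.64 min: 1 − 10.64²/(2 × 13.55²) = 0.69. A correlation of about 0.69 or more is needed.

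**4. If the 80% refers to the simple quit-week difference.** With all correlations among the four weekly means equal to r, the quit-week difference has variance 2σ²(1−r) and the interaction contrast 4σ²(1−r), which is twice as large. The interaction SD for SOL is then 14.84 × √2 = 21.0 min, and power is about 51% at 6 min and 29% at 4.3 min. For sleep efficiency at 4.42 points it is about 42%.

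**5. A check that does not use the 80%.** For 80% power at the cited effects, the SD of the tested contrast can be at most 4.3/0.4042 = 10.6 min and 4.42/0.4042 = 10.9 points.

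**6. Baseline adjustment (for the optional part of the fix).** Let s be the correlation between baseline and quit week in the same period, c any cross-period correlation, and all variances 1. The interaction variance is 4(1−s). The variance of the quit-week drug difference adjusted for the baseline-week drug difference is 2(1−c)(1−ρ²), where ρ=(s−c)/(1−c).

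| s, c | Interaction | Adjusted | Ratio |
|---|---|---|---|
| 0.4, 0.4 | 2.4 | 1.2 | 2.0 |
| 0.8, 0.6 | 0.8 | 0.6 | 1.33 |
| 0.8, 0.4 | 0.8 | 0.667 | 1.2 |

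The ratio equals 2/(1+ρ), so the adjusted variance is never the larger of the two.

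**The case against.** The strongest reply is that one power figure quoted over a range of correlations is most naturally a worst case at r=0.4. On that reading 52% is the minimum for that contrast, and power at 4.3 min could be adequate. This stands as far as it goes: a reader might infer that the trial is underpowered for SOL, and the documents do not support that. Nor do they support the opposite. The plan does not say that the 80% is a floor, and adequacy at 4.3 min would still need r of about 0.69 or more.

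A reader might also bound SOL power at 21% to 94% (30% to 99% for sleep efficiency) by fixing the 80% at either end of the correlation range. Those are not bounds. They hold only if the 80% refers to the tested contrast at a fixed SD. If it was set for the simple quit-week difference at r=0.8 and all correlations are really 0.4, interaction power is about 13% at 4.3 min and 17% at 4.42 points. If the correlation range was meant to differ by outcome, that calculation does not apply at all.

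Two further replies have some weight. The 4.3 min comes from a meta-analysis in adults with insomnia, not from abstaining smokers on a patch, so another target could be defensible. But the plan names such studies as its source and gives no argument for 6 min; the patch figure (d=0.28) does not supply one. Second, this is a proof-of-concept pilot with sleep as a secondary outcome, and no decision rule hangs on the SOL test. That limits the importance of the point but does not make the sentence correct.

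**Conclusion.** The point holds as missing justification; no stated figure is shown to be miscalculated. The claim of adequate power is unsupported for SOL: 6 min exceeds both cited effects, no SD is given, and the tested contrast is not identified. For sleep efficiency the gap is modest (5% against 4.42% and about 5%), though the SD is missing there too.

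The size depends on the reading. At 4.3 min, power is about 52% if the 80% is exact for the tested contrast, 52% to 94% if it is a floor at r=0.4 with a fixed SD, and about 29% for the interaction if the 80% describes the simple quit-week difference with equal correlations. The documents do not say which applies, so actual power is not established. The consequence is confined to interpretation of the sleep results; the primary outcome, days abstinent, is unaffected. The sentence should be fixed, at the cost of a paragraph.

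**What to change.** **(a) Correct the power statement.** Withdraw the adequacy claim for Aim 2, for SOL in particular. Justify 6 min or drop it. State power at 4.3 min and 4.42% for the contrast that will be tested, with the SD and correlations used. Until those inputs are given, write only: *If the stated 80% is exact for the tested contrast, power is about 52% at 4.3 min and 70% at 4.42%; no SD is stated, so actual power is not established.* Do not quote 21–94% or 30–99% as bounds. Do not enrol more participants. Cost: one reworded paragraph, and possibly a less favourable power figure for SOL.

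**(b) Optional improvement, not the correction of an error.** Before unblinding, prespecify a regression of the ramelteon-minus-placebo quit-week difference on the ramelteon-minus-placebo baseline-week difference, with the baseline difference centred at zero (no drug difference) so that the intercept is the drug effect. Still report the drug-by-week interaction and its p-value. Under equal variances the adjusted contrast has a variance no larger than the interaction's; in the three cases shown the interaction's is 1.2 to 2.0 times as large. Cost: one extra regression and about one degree of freedom, using baseline-week data already collected. If (b) is adopted as the main test, the power in (a) should be given for that contrast; otherwise for the interaction.

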Participants will be recruited from two sources. Participants who have previously completed studies at our center and have agreed to be re-contacted for future studies will be contacted and invited to participate in this study. Additional recruitment via TV, newspaper, radio, poster, and internet-based advertising (e.g., in-app ads, Craigslist, and iConnect) will be used to invite smokers from the general population.

STUDY DESIGN

1. Phase

Phase: II Randomized, double-blind, placebo-controlled trial

Figure 1. Overview of Study Design

PHASE	INTAKE	STUDY PERIOD 1					WASHOUT	STUDY PERIOD 2										
WEEK #	0	Baseline 1			Quit Week 2		3-4	Baseline 5			Quit Week 6							
STUDY VISITS	X	M	W	F	M	T	W	TH	F	NONE	M	W	F	M	T	W	TH	F
MEDICATION	NONE			*RAM plus TN or PLA plus TN		NONE WASHOUT			*RAM plus TN or PLA plus TN									
ACTIVITY	Medical History Psych Screen	Monitoring Visits Sleep Monitoring		Observation Assessments Sleep Monitoring		NONE			Monitoring Visits Sleep Monitoring	Observation Assessments Sleep Monitoring								
SMOKING STATE	Smoking Ad Libitum			Monitored Abstinence		Smoking Ad Libitum			Monitored Abstinence									

* Treatment (RAM vs PLA) order randomized and counterbalanced across subjects; All subjects receive transdermal nicotine (TN). TQD=Target Quit Date

2. Design

We propose to conduct a randomized, placebo-controlled, cross-over design with one within-subjects factor of medication (RAM vs. PLA; order counterbalanced). Each phase includes: 1 week of *ad libitum* smoking (baseline) and 1 week of medication (8mg RAM or PLA) plus TN while trying to abstain (quit assessment) (Figure 1).

3. Study Duration

Estimated length of time to enroll all subjects and complete the study

Enrollment will start in October 2015 (after IRB approval is received). We estimate that we will need to telephone screen 1500 smokers to enroll (consent) 150 smokers into the study (accounting for 10% eligibility). Using a conservative estimate of attrition (50%), we expect to have 50 participants complete all sessions and study requirements. We estimate enrolling 4-5 smokers per month.

Length of a subject’s participation time in study

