At the first (Monday) visit of Baseline Week 1 and 5, the participant will receive his or her SensewearPro® armband. At Baseline Week 1, the participant will receive an instructional packet and a research staff member will review how to use the armband and charger correctly.

The third (Friday) visit of each Baseline Week will last approximately 40 minutes. During this visit, subjects will:

1. Provide urine specimens for drug and (if applicable) pregnancy tests (Friday visit only). Participants who test positive for either the urine drug screen and/or pregnancy test will be withdrawn from the study.

2. Meet with a smoking cessation counselor for a 20-min coaching session to prepare them for the practice quit attempt. The counselor will review coping strategies for managing triggers and withdrawal symptoms.
3. Participants will receive their study medication and nicotine patches. Study staff will review instructions for taking the study medication and applying the nicotine patches.

These sessions can be scheduled for any time of day. Ideally, the subsequent sessions would be at the same time of day, but can be scheduled up to 3 hours earlier or later. However, the sessions may go beyond 3 hours as determined by PI discretion.

- Quit Assessment Weeks (Weeks 2 and 6). Participants will attend a 20 minute study visit every weekday of their quit assessment week. They will be asked to bring their study medication to this visit to verify medication adherence/pill counts. During this session, which will last approximately 20 minutes, participants will complete measures of:
 1. Blood pressure (See Blood Pressure Procedures under Screening/covariate measures)
 2. CO breath sample
 - a. To increase abstinence motivation, participants will receive \$10/day (in cash) for each day for self-reported abstinence that is biochemically-confirmed. On Monday, a CO reading of less than 10ppm or less than 50% of CO breath sample taken during the Baseline week will be sufficient as biochemically-confirmed abstinence. At all other visits, a CO reading less than 5 ppm will be considered as biochemically-confirmed abstinence.
 3. BrAC sample
 4. Smoking rate (timeline followback; TLFB)
 5. Medication adherence (pill count)
 6. Side effects and concomitant medication review
 - a. If moderate to severe adverse events are reported, the PI/Study Physician will be consulted and a decision will be made as to whether to proceed with the study.

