The Project Manager, PI ([name]) and Study Physician will work together to confirm eligibility criteria. The Study Physician and PI ([name]) will review charts for each subject on an ongoing basis and will document reviews by initialing and dating each chart, case report forms that contain blood pressure and heart rate measurements, and the medical history and physical form.

The research staff and Project Manager will ensure all medication is properly ordered and received from IDS, stored at the center, labeled, and distributed to subjects.

[name]. is responsible for both staff training and continuing review of completed MINI and C-SSRS interviews.

The data managers will be responsible for creating all CRFs and ensuring that all data will be entered and stored in a manner consistent with the design of the approved CRFs. They will also be responsible for developing the data entry/quality control producers for this study.

Enrollment will be complete when 50 subjects complete all study requirements. On average, 2-3 subjects will be enrolled per month. During the course of the study, safety and data quality monitoring will be performed on an ongoing basis in accordance with the University of Pennsylvania Sponsor-Investigator Standard Operating Procedure PM 504 and any findings will be reviewed on a regular basis with the Investigators at the regular study meeting. The monitoring will include a regular assessment of the number and type of serious adverse events. The first monitoring day will occur no more than two weeks after the first subject is entered.

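### The primary (H1) model for this crossover has no period term; adding one costs one degree of freedom and guards against a period effect of unknown size

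*Combined protocol and SAP*

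**What the plan says.** The design is a two-period, two-treatment crossover. Under Characteristics of the Study Population, 2. Accrual: "Enrolled participants will be randomized to receive ramelteon and placebo in counterbalanced order". Study Design, 2. Design names a single within-subject factor, medication, with order counterbalanced.

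The primary analysis is in 2. Statistical Analysis (after section 3.4), under Aim 1: "a within-subject ANOVA will test the primary hypothesis for effects of RAM (vs. PLA) on number of days abstinent during the quit week". Medication is the only effect named. The one remark about period in the analysis text belongs to the Aim 2 sleep ANOVAs, where each quit week is set against the baseline week of the same period: "Thus, each period has its own baseline control comparison". The covariates listed there are for the H2b regressions.

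On sample size, the same section says: "Fifty subjects provide 80% power to detect a difference of 0.55 days between RAM and PLA, using a SD of 1.36", with a within-subject correlation of 0.78. Section 4.1 fixes the stopping point: "Enrollment will be complete when 50 subjects complete all study requirements". Accrual explains the planned losses: of 75 eligible smokers, the investigators "conservatively estimate 25% attrition to have 50 smokers complete the study". No section requires the completers to be balanced by order.

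**The concern.** Counterbalancing protects the treatment contrast from a period effect only on average, or when the two orders are equal among those analysed. It does not remove the period effect from the residual. A two-level within-subject ANOVA with medication alone is a paired t test on the ramelteon-minus-placebo differences. A period effect pushes those differences down in one order group and up in the other, and the test counts that spread as noise.

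A period effect is plausible here. On the Friday of each baseline week, participants "Meet with a smoking cessation counselor for a 20-min coaching session to prepare them for the practice quit attempt", so the second attempt follows a coached rehearsal. H1 has no same-period baseline to lean on, because its outcome exists only in the quit week and the baseline week is ad libitum smoking.

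Two things are at stake: power when the orders are equal, and a chance shift of the estimate in the trial at hand when they are not.

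**Working it through.** **Inputs from the documents:** N = 50 completers, detectable difference 0.55 days, SD 1.36, within-subject correlation 0.78, alpha 0.05 (2. Statistical Analysis, Sample size); 75 eligible and 25% attrition (Accrual). **Assumed:** two-sided test, 1:1 allocation to order, and a period effect p (period 2 minus period 1) of 0.1, 0.25, 0.5 or 1.0 day, because the documents give none.

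**1. The plan's own figure.** For a paired t test with n = 50 and 49 df (noncentral t):
- With 1.36 as the SD of the paired differences, SE = 1.36/sqrt(50) = 0.192 and power at 0.55 is 80.04%. This reproduces the stated 80%.
- With 1.36 as the per-condition SD, SD of differences = 1.36 x sqrt(2 x (1 - 0.78)) = 0.902 and power is 98.8%. This does not reproduce it.

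Both readings are carried forward.

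**2. How period enters.** Let d = RAM - PLA and let delta be the true difference. The mean of d is delta - p in the RAM-first group (n1) and delta + p in the PLA-first group (n2).
- Expected unadjusted estimate: delta - p(n1 - n2)/N.
- Expected sample variance of d at 25:25: SD^2 + p^2 x 50/49. With SD 1.36 and p = 0.5 this is 1.8496 + 0.2551 = 2.105, 1.138 times the variance with no period effect. At p = 1.0 it is 2.870, or 1.552 times.
- With a period term, the estimate is the simple average of the two group means of d, so p cancels. Its SE is (SD/2) x sqrt(1/n1 + 1/n2), on 48 df.

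**3. Equal orders (25:25), delta 0.55, simulated, normal differences.**

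| p (days) | Power, no term, SD 1.36 | Type I error, no term, SD 1.36 | Power, no term, SD 0.902 |
|---|---|---|---|
| 0 | 80.0% | 5.0% | 98.8% |
| 0.1 | 79.8% | 4.9% | 98.8% |
| 0.25 | 79.0% | 4.6% | 98.6% |
| 0.5 | 76% | 3.7% | 97.6% |
| 1.0 | 64% | 1.5% | 90% |

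With the term, power is 80% (SD 1.36) or 98.8% (SD 0.902) throughout, and type I error is about 5%.

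**4. How unequal could the orders be?** Two starting points cover the accrual text: 75 eligible falling to 50, or 50/0.75 = 66.7, so 67 falling to 50 at 25% attrition. If loss is random with respect to order (hypergeometric, starting 38:37 or 34:33):
- exactly 25:25: probability 0.19 to 0.22;
- 28:22 or worse: 0.17 to 0.23;
- 30:20 or worse: 0.01 to 0.03.

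**5. Unequal orders, SD 1.36.**
- At 28:22 the shift is p x 6/50. For p = 0.25 it is 0.03, so the expected estimate is 0.52 or 0.58, depending on which order is larger, with power 75% or 83%. For p = 0.5 the shift is 0.06: estimate 0.49 or 0.61, power 66% or 85%. With the term, the estimate is 0.55 and power 79%.
- At 30:20 the shift is p x 10/50. Type I error without the term is 5.3%, 6.3% and 8.2% at p = 0.25, 0.5 and 1.0; with it, about 5%.

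**6. Averaged over random loss, SD 1.36.** Power without the term is 78-80% (p = 0.25), 75-77% (0.5) and 60-66% (1.0), against 80% with it. Type I error without the term is 4.8% or less.

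**7. Bounded outcome.** With a latent normal rounded and clipped to 0-5 (SD of differences about 1.4, 25:25), power without the term is 79%, 75% and 59% at p of about 0.25, 0.5 and 1.0. With it, power is 80%, 79% and 76%.

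**8. Cost if there is no period effect (SD 1.36).** Power goes from 80.04% (49 df) to 80.01% (48 df) at 25:25. The loss is about 0.5 point at 28:22 and 1.6 points at 30:20.

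**The case against.** The strongest reply is that validity is not threatened. With equal orders the estimate is unbiased and the test conservative. Averaged over random loss, type I error stays below 5%. It exceeds 5% only with a clear imbalance such as 30:20, which has probability 0.01 to 0.03, combined with a period effect of 0.25 day or more. All of this stands, and it is why the point is an improvement and not an error.

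The period effect is also assumed. Both periods follow the same schedule, with a washout and return to smoking between them, and a 1.0-day effect would be nearly twice the 0.55-day drug effect. At 0.1 day or less the term is neutral or costs a fraction of a point. At 0.25 day the average gain is roughly 0.2 to 1.4 points. If 1.36 is the per-condition SD, power without the term is still 97.6% at 0.5 day with equal orders. These points stand too: the benefit is conditional and may be nil.

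The same-period baseline in H2a is only a partial control. It removes a shift common to both weeks of a period, but not one confined to the quit week. That is correct, and H2a names no period term either; it does not help H1.

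Finally, the 76% with the term in the bounded check might suggest that the term fails at large effects. It does not show a leftover period effect: 76% is about what the realised difference and SD in that setting give.

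**Conclusion.** The point holds, as a free improvement. The H1 model omits period although order is a randomised feature of the design, and nothing elsewhere in the document supplies it. The loss is negligible for period effects of 0.1 day, about one power point at 0.25 day, about 4 points at 0.5 day and about 16 at 1.0 day, with equal orders and an SD of differences of 1.36. It is much smaller if the SD of differences is 0.90. With unequal orders there is also a chance shift of the estimate of p(n1 - n2)/N. Under random loss this is not a systematic bias.

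The conclusion rests on an assumed range for the period effect, 1:1 allocation to order, random loss and two-sided testing. That the model lacks the term, and that including it costs one degree of freedom, depends on neither the size of the period effect nor the pattern of loss.

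**What to change.** In 2. Statistical Analysis, replace the Aim 1 sentence with, for example:

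> For Aim 1 (H1), days abstinent in the quit week will be analysed by ANOVA with participant as block and with medication (RAM, PLA) and period (1, 2) as within-participant fixed effects.

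This is equivalent to comparing the period differences between the two order groups. Report the number of completers in each order. The design descriptions that name medication as the one within-subject factor can stay as statements of the experimental factor, with period identified as an adjustment term in the analysis section.

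The cost is one sentence and one degree of freedom (49 to 48). If there is no period effect, the power loss is the one given in step 8 of the working: none that matters at 25:25 and under 2 points at 30:20. No new data are needed, because period is fixed by the visit schedule. The change should be made before unblinding, so that nobody later has to choose between adjusted and unadjusted results.
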